**Investigator Interests:**

Does the principal investigator, or do any research personnel who are responsible for the design, conduct or reporting of this project or any of their family members (spouse or dependent child) have an incentive or interest, financial or otherwise, that may affect the protection of the human subjects involved in this project, the scientific objectivity of the research or its integrity? Note: The Principal Investigator (Project Director), upon consideration of the individual's role and degree of independence in carrying out the work, will determine who is responsible for the design, conduct, or reporting of the research.

See Disclosures and Management of Personal Interests in Human Research

<http://www.yale.edu/hrpp/policies/index.html#COI>

Yes       No

Do you or does anyone on the research team who is determined by you to be responsible for the design, conduct or reporting of this research have any patent (sole right to make, use or sell an invention) or copyright (exclusive rights to an original work) interests related to this research protocol?

Yes       No

If yes to either question above, list names of the investigator or responsible person:

*The Yale University Principal Investigator, all Yale University co-investigators, and all Yale University individuals who are responsible for the design, conduct or reporting of research must have a current financial disclosure form on file with the University's Conflict of Interest Office. Yale New Haven Hospital personnel who are listed as con-investigators on a protocol with a Yale University Principal Investigator must also have a current financial disclosure form on file with the University's Conflict of Interest Office. If this has not been done, the individual(s) should follow this link to the COI Office Website to complete the form:*

<http://www.yale.edu/coi/>

NOTE: The requirement for maintaining a current disclosure form on file with the University's Conflict of Interest Office extends primarily to Yale University and Yale-New Haven Hospital personnel. **Whether or not they are required to maintain a disclosure form with the University's Conflict of Interest Office, all investigators and individuals deemed otherwise responsible by the PI who are listed on the protocol are required to disclose to the PI any interests that are specific to this protocol.**

|  |
|--|
| SECTION II: GENERAL INFORMATION |
|--|

1. **Performing Organizations:** Identify the hospital, in-patient or outpatient facility, school or other agency that will serve as the location of the research. Choose all that apply:

**c. Additional Required Documents (check all that apply):**

- |  |                              |
|--|------------------------------|
|  *YCCI-Scientific and Safety Committee (YCCI-SSC)  |  N/A |
|  *Pediatric Protocol Review Committee (PPRC)   | Approval Date:               |
|  *YCC Protocol Review Committee (YRC-PRC)  | Approval Date:               |
|  *Dept. of Veterans Affairs, West Haven VA HSS   | Approval Date:               |
|  *Radioactive Drug Research Committee (RDRC)   | Approval Date:               |
|  YNHH-Radiation Safety Committee (YNHH-RSC)  | Approval Date:               |
|  Magnetic Resonance Research Center PRC (MRRC-PRC)   | Approval Date:               |
|  YSM/YNHH Cancer Data Repository (CaDR)  | Approval Date:               |
|  Dept. of Lab Medicine request for services or specimens form  |                              |
|  Imaging on YNHH Diagnostic Radiology equipment request form (YDRCTO request) found at http://radiology.yale.edu/research/ClinTrials.aspx |                              |

*\*Approval from these committees is required before final HIC approval is granted. See instructions for documents required for initial submission and approval of the protocol. Allow sufficient time for these requests. Check with the oversight body for their time requirements.*

2. **Probable Duration of Project:** State the expected duration of the project, including all follow-up and data analysis activities.

3. **Research Type/Phase: (Check all that apply)**

**a. Study Type**

- Single Center Study  
 Multi-Center Study

Does the Yale PI serve as the PI of the multi-site study? Yes  No

- Coordinating Center/Data Management

Other:

- b. **Study Phase**  N/A  
 Pilot  Phase I  Phase II  Phase III  Phase IV  
 Other (*Specify*)

4. **Area of Research: (Check all that apply)** Note that these are overlapping definitions and more than one category may apply to your research protocol. Definitions for the following can be found in the instructions section 4c:

- Clinical Research: Patient-Oriented  Clinical Research: Outcomes and Health Services  
 Clinical Research: Epidemiologic and Behavioral  
 Translational Research #1 (“Bench-to-Bedside”)  Interdisciplinary Research  
 Translational Research #2 (“Bedside-to-Community”)  Community-Based Research

5. Is this study a clinical trial? Yes  No

*NOTE the current ICMJE (International Committee of Medical Journal Editors) definition of a clinical trial: “any research study that prospectively assigns human participants or groups of humans to one or more health-related interventions to evaluate the effects on health outcomes.” Health-related interventions include any intervention used to modify a biomedical or health-related outcome (for example, drugs, surgical procedures, devices, behavioral treatments, dietary interventions, and process-of-care changes). Health outcomes include any biomedical or health-related measures obtained in patients or participants, including pharmacokinetic measures and adverse events”*

If yes, where is it registered?

- Clinical Trials.gov registry  Upon funding will be registered in clinical trials.  
 Other (*Specify*)

Registration of clinical trials **at their initiation** is required by the FDA, NIH and by the ICMJE.

*If this study is registered on [clinicaltrials.gov](http://clinicaltrials.gov), there is new language in the consent form and compound authorization that should be used.*

For more information on registering clinical trials, including whether your trial must be registered, see the YCCI webpage, <http://ycci.yale.edu/researchers/ors/registerstudy.aspx> or contact YCCI at [contact])

6. Does the Clinical Trials Agreement (CTA) require compliance with ICH GCP (E6)?  
 Yes  No

7. Will this study have a billable service? A Billable Service is defined as a service or procedure that will be ordered, performed or result in charging in EPIC for individuals who are enrolled in

a clinical research study, regardless if the charge is intended to be paid by the subject/their insurance or the research study.

Yes  No

If you answered "yes", this study will need to be set up in OnCore Support  
<http://medicine.yale.edu/ymg/systems/ppm/index.aspx>

8.. Are there any procedures involved in this protocol that will be performed at YNHH or one of its affiliated entities? Yes \_\_\_ No X *If Yes, please answer questions a through c and note instructions below. If No, proceed to Section III.*

a. Does your YNHH privilege delineation currently include the **specific procedure** that you will perform? N/A

b. Will you be using any new equipment or equipment that you have not used in the past for this procedure? No

c. Will a novel approach using existing equipment be applied? N/A

If you answered “no” to question 7a, or "yes" to question 7b or c, please contact the YNHH Department of Physician Services ([name]) for prior approval before commencing with your research protocol.

**SECTION III: FUNDING, RESEARCH TEAM AND TRAINING**

1. **Funding Source:** Indicate all of the funding source(s) for this study. Check all boxes that apply. Provide information regarding the external funding source. This information should include identification of the agency/sponsor, the funding mechanism (grant or contract), and whether the award is pending or has been awarded. Provide the M/C# and Agency name (if grant-funded). If the funding source associated with a protocol is “pending” at the time of the protocol submission to the HIC (as is the case for most NIH submissions), the PI should note “Pending” in the appropriate section of the protocol application, provide the M/C# and Agency name (if grant-funded) and further note that University (departmental) funds support the research (until such time that an award is made).

| PI                      | Title of Grant  | Name of Funding Source                   | Funding   | Funding Mechanism   |
|-------------------------|---|--|---|---|
| [name] | Progesterone
Augmentation for
Smoking Cessation in
Women | National Cancer Institute
R21CA198187 |  Federal
 State
 Non Profit
 Industry
 Other For
Profit
 Other |  Grant-M# 160200
 Contract#
 Contract Pending
 Investigator/Department
Initiated
 Sponsor Initiated
 Other, Specify: |

|  |  |  |   |  |
|--|--|--|---|--|
|  |  |  |  Federal
 State
 Non Profit
 Industry
 Other For Profit
 Other |  Grant-M#
 Contract#
 Contract Pending
 Investigator/Department Initiated
 Sponsor Initiated
 Other, Specify: |
|  |  |  |  Federal
 State
 Non Profit
 Industry
 Other For Profit
 Other |  Grant-M#
 Contract#
 Contract Pending
 Investigator/Department Initiated
 Sponsor Initiated
 Other, Specify: |

IRB Review fees are charged for projects funded by Industry or Other For-Profit Sponsors. Provide the Name and Address of the Sponsor Representative to whom the invoice should be sent. *Note: the PI's home department will be billed if this information is not provided.*

#### For HIC Use Only

\_\_\_\_\_  
Date Approved

\_\_\_\_\_  
Human Investigation Committee Signature

This protocol is valid through \_\_\_\_\_

|                                 |
|---------------------------------|
| SECTION V: RESEARCH PLAN |
|---------------------------------|

**1. Statement of Purpose:** State the scientific aim(s) of the study, or the hypotheses to be tested.

This pilot randomized clinical trial will test whether modifying the hormonal milieu during the menstrual cycle through administration of exogenous progesterone will augment the effectiveness of NRT for smoking cessation in regularly cycling women. Our study hypothesis regarding progesterone's augmentation effects are supported by systematic studies conducted by our group and others. Findings from this study may lead to novel treatment approaches tailored specifically to female smokers

This study seeks to determine if modifying the hormonal milieu of the menstrual cycle, through administration of exogenous progesterone, will improve the effectiveness of treatments for smoking cessation in women. Progesterone, a gonadal hormone, is used clinically for treatment of endometrial hyperplasia, amenorrhea, dysfunctional uterine bleeding, and for assisted reproduction in women. Progesterone also shows promise for the treatment of multiple central nervous system disorders including cocaine addiction, seizure disorder, and traumatic brain injury (1, 2). The utility of progesterone for smoking cessation is suggested by a number of previous studies. In a clinical trial, progesterone dominance during the luteal phase of the menstrual cycle, as compared to estrogen dominance in the follicular phase, significantly enhanced smoking abstinence in women attempting to quit smoking (3). Our group conducted pioneering human studies to determine the safety and potential efficacy of progesterone for the treatment of nicotine addiction. In these studies, progesterone, compared to placebo, attenuated the pleasurable effects of cigarette smoking or intravenously administered nicotine in abstinent smokers (4, 5). Progesterone also reduced craving for cigarettes and improved response inhibitory function in abstinent female smokers (6). These findings are promising because attenuating nicotine reward, and improving withdrawal symptoms and response inhibition are potential treatment targets for nicotine addiction (7, 8). As the next step, we seek to determine if progesterone augments standard smoking cessation treatments (e.g., NRT) in regularly cycling women. We hypothesize that co-treatment with progesterone, compared to placebo, will enhance the effectiveness NRT for smoking cessation. To test this hypothesis, we propose an 8-week, double-blind, placebo-controlled clinical trial, which will randomize 50 smokers using a 1:1 assignment ratio to 400 mg/day progesterone or placebo. Consistent with the Clinical Practice Guidelines (9), all participants will also receive transdermal nicotine patch (TNP) plus brief counseling for smoking cessation during the study participation. The dose of TNP will be 21mg/24 hours for 4 weeks, 14mg for weeks 5 and 6 and 7 mg for weeks 7 and 8 for women who smoked at least 10 cigarettes per week. We will start a 14 mg/day dose of TNP for women who smoke less than 10 cigarettes per week.

Specific Aim #1: To determine if progesterone +TNP is superior to placebo +TNP for prolonged and 7-day point prevalence of smoking abstinence rates at the end of 8 weeks of treatment and at 1 and 3 month follow-up time points. We will also evaluate the safety and tolerability of progesterone treatment, compared to placebo. Our co-primary outcome measures will be 7-day point prevalence of smoking abstinence and breath CO at the end of treatment and 1- and 3-months after the end of the trial.

Specific Aim #2: To determine if progesterone + TNP treatment, compared to placebo + TNP, improves response inhibitory function, as assessed by the Stroop, The Go/No Go task, and the Digit Symbol Task.

Specific Aim # 3: To determine if progesterone + TNP treatment, compared to placebo + TNP, leads to a greater reduction in cigarette craving and nicotine withdrawal symptoms, as assessed

by the Questionnaire on Smoking Urges-Brief (QSU-B) and the Minnesota Nicotine Withdrawal Scale (MNWS), respectively.

Specific Aim #4: To evaluate with affective changes, as shown on the Positive and Negative Affect Schedule, mediates the effects of progesterone on smoking abstinence.

Exploratory Aim: We will evaluate the degree to which serum estradiol and progesterone levels achieved during the trial are associated with a) greater smoking abstinence, b) improved response inhibition, and c) less craving and withdrawal symptoms.

2. **Background:** Describe the background information that led to the plan for this project. Provide references to support the expectation of obtaining useful scientific data.

Nicotine addiction continues to be the main preventable cause of death in developed countries, with an estimated 435,000 premature deaths in the U.S and 5 million deaths worldwide (11). About 18% of women and 22% of men in the US smoke (11). Some evidence suggests that women respond less favorably to NRTs, even though they maintain their nicotine addiction with lower levels of nicotine intake than men (12-15). Women, compared to men, may be more vulnerable to the complications of smoking, most notably lung cancer (16, 17). In the US, lung cancer kills more women than the breast and colon cancer combined. These findings support the need to develop more effective treatments tailored for female smokers.

*Current pharmacological treatments for smoking cessation:* Current first line treatments for smoking cessation include NRT (including nicotine gum, lozenge, inhaler and spray), bupropion, and varenicline (10, 18). With some minor differences, these treatments increase the odds of quitting smoking by 2 to 3 fold (19, 20). Still, this only translates to smoking abstinence at one year for 10%-30% of smokers who attempt to quit. Combination treatments may be more effective than a single agent for smoking cessation suggesting that there is room for improved efficacy among smoking cessation treatments(21). Unfortunately, concerns about the neuropsychiatric adverse effects of varenicline and bupropion, especially suicidal ideation and behavioral changes, limit their use alone or in combination with other medications (22). Among NRTs, there are no significant differences between different products in their efficacy for smoking cessation (23). Transdermal nicotine patch (TNP) has advantages over other NRTs for its consistent delivery of nicotine for 24 hours, ease of use and favorable adverse effect profile.

*Role of sex hormones in addictive behaviors:* Both estradiol and progesterone have well-documented actions on multiple neurotransmitters affecting the brain reward pathway (24). While estradiol activates the reward pathway, progesterone has the opposite effects (25). For example, in the mid-follicular phase of the human menstrual cycle (when progesterone is low and estrogen is high), as compared to the progesterone dominant luteal phase, the reward circuitry (midbrain, striatum, and left fronto-polar cortex) is more highly activated (26). As summarized below, the therapeutic potential of sex hormones, especially progesterone, suggest that progesterone may have a role in treatment of nicotine addiction in female smokers (27).

*Progesterone as a neurosteroid:* Progesterone is a hormone produced by male and female gonads, adrenal glands and in the brain by oligodendrocytes and neurons (hence the moniker "neurosteroid") (28). In premenopausal women, progesterone levels are low in the follicular phase of the menstrual cycle, and are comparable to those in men, < 1 ng/ml (29). Women have higher progesterone levels than men during the luteal phase of the menstrual cycle (2-28

ng/ml), and during pregnancy (9 to 200 ng/ml) (30). Progesterone and its metabolites interact with multiple neurotransmitter receptors including GABAA, glycine, sigma1, kainate, serotonin3, and nicotinic receptors (31). Among these actions, the best studied are the effects of progesterone on the GABA receptors. Progesterone's active metabolites, pregnanolone and allopregnanolone, have positive modulatory effects on GABAA receptors, and enhance GABA transmission (31). This may lead to reduced nicotine reward given the inhibitory actions of GABA on dopamine release in nucleus accumbens, a key step in mediating reward (32).

*Endogenous progesterone modulates nicotine addiction:* Many preclinical studies demonstrate that progesterone administration reduces the rewarding effects of cocaine (33, 34). Although the actions of exogenous progesterone on nicotine reward have not been assessed (27), Lynch (35) showed that in adolescent rats that are trained to self-administer nicotine, levels of responding under a progressive-ratio schedule are negatively associated with plasma progesterone levels. These results support an inhibitory influence of progesterone on nicotine self-administration.

In a human laboratory study using an ad lib smoking paradigm in female smokers, a lower progesterone to estrogen ratio was associated with greater number of puffs and increased puff intensity (36). Similarly, in a clinical trial, Allen et al. (4) randomized 200 women to quit in follicular or luteal phase of the menstrual cycle. Women who quit in the follicular phase relapsed faster to smoking than those who quit during the progesterone dominant luteal phase ((OR) = 2.87, 95% CI= 1.47– 5.59). The effect was robust; at 30 days the odds of remaining abstinent for the luteal phase group was 3.18 (95% CI= 1.59–6.34) higher than the follicular phase group. This same group showed that abstinence during the luteal phase of the cycle was accompanied by increases in allopregnanolone.(37) Mazure et al. (38) produced similar findings using bupropion. However, there are divergent findings (39, 40) that may be a result of differing study methods. Our proposed study will help clarify the literature by providing exogenous progesterone rather than relying on timing of the menstrual cycle to infer hormone levels.

*Progesterone as a treatment for nicotine addiction.* Our group has conducted a series of pioneering studies demonstrating the safety and potential effectiveness of progesterone for the treatment of nicotine addiction in women. In our initial study (5), we found that oral progesterone, compared to placebo, attenuated the craving for and pleasurable or hedonic effects from smoking in 12 female smokers. In our next study, we confirmed these findings using our intravenous nicotine administration paradigm (6). We observed that progesterone attenuated the pleasurable effects of intravenous nicotine in abstinent 12 male and female smokers.

We have also evaluated underlying mechanisms of the potential therapeutic effects of progesterone (7). We found that 400 mg of progesterone treatment, administered for four days, reduced urges to smoke in female abstinent smokers. Further, progesterone treatment improved performance in the Stroop and the Digit Symbol Substitution Test (DSST) but the effect on the Stroop performance was sex specific in that only women (n=30) showed improvement. Given that the Stroop test is a measure of ability to inhibit pre-potent responses, our findings suggest that progesterone improves response inhibition in abstinent female smokers (7). Our findings are consistent with preclinical and clinical suggesting that progesterone improves response inhibition or impulsive behavior which may contribute to its proposed efficacy for smoking cessation (41, 42).

*Safety of Progesterone:* Progesterone is used treat a variety of gynecological and obstetrical disorders. Although extensive first pass effects limited oral use, oral micronized progesterone formulations are now FDA approved. The safety and tolerability of micronized progesterone is

well established (43, 44). The most common adverse effect of progesterone is mild sedation. Other less common adverse effects include menstrual irregularity, spotting or breakthrough bleeding, dizziness, cramps, nausea, fatigue, headache, and breast tenderness (44, 45). In our previous studies, micronized progesterone has been well tolerated without any serious adverse events (2, 5-7, 46-49).

Progesterone is commonly confused with progestins, a group of synthetic progesterone analogs that include medroxyprogesterone and norethindrone, are included in most oral contraceptives and some hormone replacement therapies. Progestins differ from natural progesterone in their pharmacological properties and side effect profiles. Most progestins, but not progesterone, have well-characterized androgenic, glucocorticoid, and anabolic effects and have been associated with unfavorable side effects including fluid retention, alterations in lipid profile, and increase risk for breast cancer and cardiovascular events. These side effects are not associated with natural progesterone treatment (50-52). An additional key difference between progesterone and most progestins is that the former, but not the latter, are metabolized to pregnanolone and allopregnanolone, which, as noted above, have significant GABAergic and other CNS effects. Consistent with these distinctions, progestins and progesterone differ in their influence on many CNS functions including learning, memory, and reward functions (53). Finally, progesterone (but not progestins) is also under investigation for the treatment of cocaine addiction, seizure disorder, and traumatic brain injury (54, 55).

*Summary of the rationale:* Progesterone's capacity to attenuate smoking urges, to diminish the positive subjective effects of smoking, and to improve cognitive performance all point to its potential therapeutic value for smoking cessation. Because smoking urges predict relapse to smoking, progesterone-related attenuation supports its potential efficacy for smoking cessation (56). Greater positive subjective effects from smoking before a quit attempt or during a lapse also predict relapse to smoking (57, 58). Similarly, improvement of cognitive function in association with progesterone use, especially with regard to response inhibition is a potential mechanism for the proposed efficacy of progesterone for smoking cessation (59).

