#### *Human subjects*

**Recruitment:** Recruitment will take place over 1.5 years, requiring enrollment of approximately 2-3 subjects per month. In our previous studies, we have been able to recruit on average 4 female smokers per month. Recruitment is further explained in Human Subjects but will be accomplished by direct screening in our reproductive health centers (20% of women seen for services in these centers are smokers), direct mail invitations, posters and flyers placed in local obstetrician-gynecologist offices. We have successfully used these techniques to recruit substance users, smokers and women with premenstrual dysphoric disorder in prior clinical trials. [name] has a secondary appointment in Obstetrics & Gynecology and has conducted numerous studies that entailed screening women in the reproductive health settings of Yale New Haven Hospital and their faculty (see Biosketch).

Update June 2017: All participants had blood levels of progesterone drawn. We were blind to assignment of participants but at the end of the study found that those who were randomized to active progesterone had low progesterone levels. This could be due to the progesterone preparation or the fact that smokers metabolize it very quickly. In any case, the low progesterone levels in the active treatment group obviates our ability to test our hypothesis that progesterone augmentation assists abstinence for smokers. Given the lack of funds, we cannot repeat the project. Rather, we are recruiting a second cohort and are using a commercially available oral micronized progesterone rather than the previous medication that was compounded for the study. We plan to enroll a minimum of 12 people with an imbalanced ratio of 6 active to 1 placebo. We will continue to obtain plasma levels of progesterone. This will enhance our ability to test our hypothesis. If need be in a final analysis, and give that this is a pilot project, we may be able to use the participants randomized to placebo in the first cohort and second cohort and the participants randomized to active in the second cohort.

Update September 2017: We request an additional blood draw (timeline is around Visit #6 or #7 to confirm progesterone plasma levels and compliance with pill taking. The second blood draw will be the same as the first one, completed at a professional lab on the first floor of the research site building. Approximately 6 ccs of blood will be drawn for each.

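### Low serum progesterone is said to make the hypothesis untestable whatever its cause; this holds if delivery failed but does not follow if smokers metabolise the drug quickly

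*Combined protocol and SAP*

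**What the plan says.** The Background (Section V.2, on progesterone as a neurosteroid) says that "Progesterone and its metabolites interact with multiple neurotransmitter receptors including GABAA" and several others. It then singles out the GABA effects as the best studied, stating that progesterone's "active metabolites, pregnanolone and allopregnanolone, have positive modulatory effects on GABAA receptors, and enhance GABA transmission". The next step is the link to smoking: "This may lead to reduced nicotine reward given the inhibitory actions of GABA on dopamine release in nucleus accumbens". Later in the Background, conversion is given as a key difference between progesterone and most progestins: "the former, but not the latter, are metabolized to pregnanolone and allopregnanolone". The same section cites a study in which luteal-phase abstinence came with a rise in allopregnanolone.

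Section V.1 states the hypothesis as co-treatment with progesterone, compared with placebo, enhancing the effectiveness of nicotine replacement. It is to be tested by randomising 50 smokers 1:1 to 400 mg/day or placebo.

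The June 2017 update in Section V.3 (Human subjects) reports low progesterone in women randomised to active drug and says: "This could be due to the progesterone preparation or the fact that smokers metabolize it very quickly". It concludes: "In any case, the low progesterone levels in the active treatment group obviates our ability to test our hypothesis". Section VI.A.2 repeats both sentences. The response is a second cohort on a commercial product (at least 12 women, 6 active to 1 placebo), with plasma progesterone measured again. If need be, a final analysis may use placebo women from both cohorts and active women from the second only.

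Progesterone and estradiol are the only hormones named for measurement (for example, the Exploratory Aim in Section V.1 asks whether "serum estradiol and progesterone levels achieved during the trial are associated with" the outcomes). No metabolite assay is planned.

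**The concern.** The update draws one conclusion from two explanations that have different consequences. If too little drug was absorbed, the first cohort did not receive the intervention. If smokers clear progesterone quickly, the drug was delivered and converted, and the products of conversion are among the species the Background calls active. Rapid clearance would also be a property of the population the treatment is meant for, so the randomised comparison would still address whether giving progesterone helps smokers quit.

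The inference has a practical use in the plan. It is the stated ground for the second cohort and for an optional final analysis that sets aside the first cohort's randomised active arm while keeping its placebo arm. If the inference fails for one of its own two explanations, low serum progesterone alone does not justify that choice. Changing the product answers the preparation explanation but not the metabolism explanation, because the second cohort also consists of smokers.

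**Working it through.** The plan gives no figure to reproduce here: it reports no progesterone values, no threshold for low and no metabolite data. The check is mainly one of logic, with a small model to show what is and is not determined.

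**Step 1: each cause set against what it implies.**

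| Cause of low progesterone | Parent hormone | Active metabolites | Does low parent show that the proposed route was not engaged? |
|---|---|---|---|
| Preparation failed (first stated cause) | low | low | yes |
| Missed doses (not listed in the update; the added blood draw is partly to check pill-taking) | low | low | yes |
| Rapid metabolism (second stated cause) | low | not determined | no |

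The conclusion follows in the first two rows and fails in the third.

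**Step 2: how far metabolite exposure is undetermined.** Take a linear model at steady state. Let D be the dose, T the dosing interval, F the fraction absorbed, f the fraction converted, CL the parent clearance and CLm the metabolite clearance.

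- Mean parent = F × D / (CL × T)
- Mean metabolite = F × f × D / (CLm × T)

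Multiply CL by k and hold F, f, D and T fixed. Mean parent becomes 1/k of usual. Mean metabolite does not contain CL, so it changes only if CLm changes:

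| Parent clearance | Mean parent | Mean metabolite, CLm unchanged | Mean metabolite, CLm also × k |
|---|---|---|---|
| usual (k = 1) | 100% | 100% | 100% |
| doubled (k = 2) | 1/2 = 50% | 100% | 1/2 = 50% |
| tripled (k = 3) | 1/3 = 33% | 100% | 1/3 = 33% |

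The 100% column results from holding absorption, conversion and metabolite clearance constant; it is not evidence that metabolite levels were normal. The last column rests on an equally unsupported assumption. The two are illustrative cases, not bounds: a lower converted fraction would reduce metabolite further. The same low parent level is compatible with quite different metabolite exposures, and the documents do not say which applies.

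**Step 3: what rests on the inference.**

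- First-cohort active arm at target: 50 × 1/2 = 25 women. The number actually enrolled is not reported.
- Second cohort at its minimum: 12 × 6/7 = 10.3 active and 12 × 1/7 = 1.7 placebo, so about 10 and 2.
- Optional final analysis: about 10 active (second cohort only) against 25 + 2 = about 27 placebo. The active women and most of the placebo women would then come from different cohorts and would not have been randomised against each other.

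**The case against.** The strongest reply is that the trial's stated purpose is to modify the hormonal milieu. The Background contrasts giving progesterone with inferring hormone levels from cycle timing. Twice-daily dosing is chosen to keep plasma progesterone stable. It also cites plasma progesterone in rats and the progesterone-to-estrogen ratio in women. On that reading, low plasma progesterone means the intended change was not shown, whatever the cause. This stands in part: for a hypothesis strictly about circulating progesterone, the update's sentence is consistent. But Section V.1 also states the hypothesis as co-treatment versus placebo in smokers, and the update itself words it as progesterone augmentation assisting abstinence. The first cohort's randomised comparison addresses that form.

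Several stronger readings are tempting and not supported:

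- A reader might infer that the protocol credits the effect mainly to the metabolites. It does not apportion it: parent and metabolites are named together, the GABA route is offered as a possibility, and the closing summary of the rationale does not mention metabolites. The remark "Although extensive first pass effects limited oral use" is presented as a limit on oral use, not as a source of activity.
- A reader might infer that the first cohort was adequately exposed. Rapid metabolism does not show that; metabolites may also be cleared quickly or formed less.
- A reader might infer that a null result is being written off, or that the second cohort would be dismissed in the same way. No efficacy result for the first cohort is reported, and omission of its active arm is conditional.
- A reader might fault the Exploratory Aim. It already names serum estradiol and progesterone, and nothing says a null association would be read as no hormone effect.
- A reader might measure the harm by the wider confidence interval of the optional analysis. That reflects a change of analysis set, not this inference.

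**Conclusion.** The point holds in limited form. The update's conclusion is sound for failed delivery and does not follow for rapid metabolism, one of its two stated causes. Low serum progesterone alone neither shows nor excludes adequate exposure, so it is not sufficient ground for leaving the first cohort's randomised active arm out of the final analysis.

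This rests on the protocol's own naming of pregnanolone and allopregnanolone as active, on its statement of the hypothesis as a treatment comparison, and on the absence of any planned metabolite measurement. It does not rest on the model, which only shows that the metabolite level is undetermined. The size is one arm, 25 women at target, in a pilot trial where omitting that arm is so far only an option. It should be corrected because the unqualified sentence appears twice and the correction is cheap.

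**What to change.** 1. In Section V.3 (Human subjects) and Section VI.A.2, restrict the statement that the hypothesis cannot be tested to failed delivery, whether through the preparation or missed doses. Say that under rapid metabolism the question remains open, and that the change of product does not address that explanation.
2. Add that low serum progesterone alone does not classify a woman, an arm or a cohort as unexposed, and is not a ground for leaving out the first cohort's active arm.
3. In Section V.12, state that the first cohort's randomised comparison will be reported as randomised, and that any analysis omitting its active arm is exploratory. This fits the commitments in Section V.12 to CONSORT reporting and in Section V.3 to following the full randomised sample.
4. Optional, if serum is available and funds allow: assay allopregnanolone on blood already being drawn. Low parent with low metabolite would point towards the product or missed doses; low parent with preserved metabolite would point towards metabolism. The documents do not say whether serum is kept, and the update cites lack of funds, so items 1 to 3 do not depend on this.

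Items 1 to 3 cost a few sentences and one labelled analysis, with no change to visits, procedures or treatment. Item 4 costs one assay.
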